8.3.9.2. Exploratory Analyses of Peanut Allergy Status in LEAP Siblings

Factors affecting peanut allergy status

The peanut allergy status of LEAP Trio Siblings in the ITT populations will be analyzed using logistic regression models with a random family effect and possible fixed effects including treatment arm, whether Younger or Older sibling, age at V144, TEWL measurement, sibling history of eczema, whether resided in home of LEAP Participant on or before V60, peanut protein in bed dust at V144, peanut protein in bed dust of LEAP Participant at V60, peanut consumption of the sibling during the first year of life, and peanut consumption of LEAP

Participant during the LEAP study. The fixed effects, along with possible interactions terms, will be evaluated for inclusion in the final logistic regression model.

8.3.10. Secondary Endpoint 8: Peanut-related adverse events

Adverse events will be collected from participants in all 4 cohorts (LEAP Participants, Older Siblings, Younger Siblings, and Parents) from the time the participant signs the informed consent until the participant completes study participation. Since the LEAP Trio study consists of a single planned study visit, the principal aim is to capture adverse events that may be related to study procedures such as venipuncture, home self-blood collection, skin-prick testing, assessment of TEWL, and oral food challenges. Peanut-related adverse events will be reported from reactions experienced during or within 30 days after the peanut oral food challenges. Peanut oral food challenges will be conducted in LEAP Participants and LEAP Siblings < 18 year of age.

8.3.10.1. LEAP Participants

The proportion of participants experiencing at least one peanut-related adverse event will be compared between LEAP Consumers and LEAP Avoiders using a logistic regression model.

8.3.10.2. LEAP Siblings

The proportion of participants experiencing at least one peanut-related adverse event will be compared between the siblings of the LEAP Consumers and LEAP Avoiders using a logistic regression model with a random family effect included to account for the clustering of siblings within family units and the analysis of multiple siblings. Older Siblings and Younger Siblings will be analyzed separately.

8.4. Exploratory Endpoints

8.4.1. LEAP Participants, Siblings, and Parents

For a listing and numbering of the exploratory endpoints, see the Protocol Summary in Section 3 above and Section 3.2.2 of the protocol V7.0. Analyses of the exploratory endpoints are summarized in Table 8.4.1 below. Details of the exploratory endpoint analyses are provided in sections 8.4.2 through 8.4.5.

Table 3: Overview of the Exploratory Endpoints

Secondary Endpoint	LEAP Participant Analysis	LEAP Sibling Analysis	LEAP Parent Analysis
Exploratory 1	The proportion of participants with food allergies other than peanut will be summarized descriptively.	The proportion of siblings with food allergies other than peanut will be summarized descriptively.	The proportion of parents with food allergies other than peanut will be summarized descriptively.
2	Dietary assessments will be compared between LEAP avoiders and LEAP consumers using parametric and non-parametric tests (e.g. Wilcoxon and t-test). The data will first be		

Secondary Endpoint	LEAP Participant Analysis	LEAP Sibling Analysis	LEAP Parent Analysis
	tested to determine normality. If the data are not normal then a Wilcoxon test will be run. If the data are normal then tests will be run to determine if the variances are equal between the two groups. If the variances are equal, a two sample t-test assuming equal variances will be used; otherwise, a two sample t-test assuming unequal variances will be used.		
3	TEWL will be compared between LEAP avoiders and LEAP consumers using parametric and non-parametric tests (e.g. Wilcoxon and t-test). The data will first be tested to determine normality. If the data are not normal then a Wilcoxon test will be run. If the data are normal then tests will be run to determine if the variances are equal between the two groups. If the variances are equal, a two sample t-test assuming equal variances will be used; otherwise, a two sample t-test assuming unequal variances will be used.	TEWL will be compared between the siblings of the LEAP avoiders and LEAP consumers using linear mixed effects models with a random family effect included to account for the nesting of siblings within family units and the analysis of multiple siblings.	
4	Exploratory endpoint #4 (household peanut consumption and concentration of peanut dust) will be compared between the families of the LEAP avoiders and LEAP consumers using linear mixed effects models with a random family effect included to account for the nesting of multiple family members within family units.		

8.4.2. Exploratory Endpoint 1: Prevalence of food allergies (other than peanut)

Food allergy history questionnaire and allergen tests will be used in all 4 cohorts (LEAP Participants, Older Siblings, Younger Siblings and Parents) to determine which participants are allergic to foods other than peanut. The proportion of participants in the ITT population with food allergies other than peanut will be summarized descriptively by LEAP Trio participant cohort and treatment arm.

8.4.3. Exploratory Endpoint 2: Dietary assessment questionnaires

A dietary history will be obtained for LEAP Participants using a 3-day food diary that captures typical food consumption around the time of V144 and provides a breakdown of macro- and micronutrient intake and total energy intake.

Dietary assessments for the LEAP Participants in the ITT population will be compared between LEAP Consumers and LEAP Avoiders using the most appropriate parametric, non-parametric or categorical tests for the data.

Results to be compared between the LEAP Consumers and LEAP Avoiders include:

- Nutrients as % of total energy intake (TE)
- Nutrients as % of reference nutrient intake (RNI)

If the data are continuous, the data will first be tested to determine normality. If the data are not normal then a Wilcoxon test will be run. If the data are normal then tests will be run to determine if the variances are equal between the two groups. If the variances are equal, a two sample t-test assuming equal variances will be used; otherwise, a two sample t-test assuming unequal variances will be used.

If the data are categorical, Fisher's exact tests, chi-square tests or logistic regression models will be used to test for associations between the LEAP Trio treatment arms (LEAP Consumers and LEAP Avoiders) and the dietary outcomes to be tested.

8.4.4. Exploratory Endpoint 3: Transepidermal Water Loss

Transepidermal water loss (TEWL) is a measure of water loss from skin and will be recorded for LEAP Participants and Siblings. Three TEWL measurements will be taken at V144 and the average of the measurements for each participant will be used in the analysis.

8.4.4.1. LEAP Participants

The average of the TEWL measurements collected at V144 for the LEAP Participants in the ITT population will be compared between LEAP Consumers and LEAP Avoiders using the most appropriate parametric or non-parametric tests (e.g. Wilcoxon and t-test) for the data. The data will first be tested to determine normality. If the data are not normal then a Wilcoxon test will be run. If the data are normal then tests will be run to determine if the variances are equal between the two groups. If the variances are equal, a two sample t-test assuming equal variances will be used; otherwise, a two sample t-test assuming unequal variances will be used.

The average of the TEWL measurements collected at V144 for the LEAP Participants in the ITT population will also be compared between LEAP Consumers and LEAP Avoiders using a linear regression model with adjustments for the following participant groups:

- Participants who have eczema vs. do not have eczema, according to the criteria in section 8.3.6
- Participants who are sensitized vs. non-sensitized to foods tested in LEAP Trio
- Participants who are sensitized vs. non-sensitized to aeroallergens tested in LEAP Trio

Sensitization to foods and aeroallergens tested in LEAP Trio will be defined as:

- Allergen specific IgE ≥ 0.35 kU/L,
- Skin prick test to allergen ≥ 3 mm.

8.4.4.2. LEAP Siblings

The average of the TEWL measurements collected at V144 for the LEAP Siblings in the ITT population will be compared between LEAP Consumers and LEAP Avoiders using a linear mixed effects model with a random family effect included to account for the clustering of

siblings within family units and the analysis of multiple siblings. Older Siblings and Younger Siblings will be analyzed separately.

8.4.5. Exploratory Endpoint 4: Household peanut consumption

Peanut consumption questionnaires will be used to determine the amount of each participant's average weekly peanut protein consumption in the 4 weeks prior to V144 for participants in all 4 cohorts (LEAP Participants, Older Siblings, Younger Siblings, and Parents), as mentioned in section 8.3.2. Household consumption questionnaires will be used to determine the amount of average weekly peanut protein consumption in the 4 weeks prior to V144 for household members who did not participate in LEAP Trio. The combination of the LEAP Trio participant and household peanut consumption questionnaires will provide a more accurate assessment of household environmental peanut exposure than in the participant questionnaires alone.

The average weekly peanut protein consumption for all members of the LEAP Participants' households will be compared between LEAP Consumers and LEAP Avoiders using a linear mixed effects model with a random family effect included to account for the clustering of members within households and the analysis of multiple household members.

8.4.6. Exploratory Endpoint 4: Concentration of peanut dust in participants' homes

Dust samples will be collected from the bed sheets of the LEAP Participants and LEAP Siblings using a vacuum pack and collection questionnaire provided to participating families. The bed dust will be analyzed to determine the amount peanut protein (mcg/g dust) in the bed dust. The amount of peanut protein in the bed dust will provide an assessment of environmental peanut exposure in the participants' homes.

The amount of peanut protein in the bed dust for the LEAP Participants and LEAP Siblings will be compared between LEAP Consumers and LEAP Avoiders using a linear mixed effects model with a random family effect included to account for the clustering of LEAP Participants and LEAP Siblings within households and the analysis of multiple household members. The average weekly peanut protein consumption prior to V144 of the participants will be included in the model as a covariate. For this analysis, LEAP Participants in the ITT population and LEAP Siblings in the ITT population will be analyzed together in the same linear mixed effects model.

The same statistical methodology will be repeated for the LEAP Participants in the ITT population and LEAP Siblings ITT population, analyzed separately.

The amount of peanut protein in the bed dust for the LEAP participants at V60, V72, and V144 will be summarized and plotted, and may be analyzed along with immunologic and clinical outcomes to explore the relationships between bed dust and treatment arm, as well as other factors.

Immunologic outcomes and other clinical outcomes will be summarized and plotted to explore the relationships with the change or stability in the peanut allergy status over time, as well as between the LEAP Consumers and LEAP Avoiders.

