Exploratory endpoint #4 (household peanut consumption and concentration of peanut dust) will be compared between the families of the LEAP avoiders and LEAP consumers using linear mixed effects models with a random family effect included to account for the nesting of multiple family members within family units.

Younger and older siblings of LEAP participants will be analyzed separately.

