6. STUDY PARTICIPANTS

For all analyses that include treatment arm, LEAP participants will be assigned to the intervention (LEAP Consumers) or control group (LEAP Avoiders) according to the prior randomized treatment assignment from the LEAP study. Siblings and parents will be assigned to the intervention or control group based on the prior randomization of their LEAP participant sibling or child, respectively.

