8.3.2.1. LEAP Participants

The average weekly peanut protein consumption prior to V144 for the LEAP Participants in the ITT population will be compared between LEAP Consumers and LEAP Avoiders using the most appropriate parametric or non-parametric tests (e.g. Wilcoxon and t-test) for the peanut consumption data. The data will first be tested to determine normality. If the data are not normal then a Wilcoxon test will be run. If the data are normal then tests will be run to determine if the variances are equal between the two groups. If the variances are equal, a two sample t-test assuming equal variances will be used; otherwise, a two sample t-test assuming unequal variances will be used.

The same statistical methodology will be repeated in the average weekly peanut consumption immediately following LEAP or LEAP-On for the LEAP Participants in the ITT population.

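### The only committed arm comparisons of V144 bed dust adjust for each person's own recent peanut intake, a post-randomisation variable, so they do not estimate the total arm difference in dust exposure; the covariate is not in Protocol 9.2.2 or SAP Table 3

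*SAP*

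**What the plan says.** SAP 8.4.6 gives the purpose of the measurement: "The amount of peanut protein in the bed dust will provide an assessment of environmental peanut exposure in the participants' homes". It then compares dust between arms in a linear mixed model with a random family effect and adds: "The average weekly peanut protein consumption prior to V144 of the participants will be included in the model as a covariate". The model is fitted to LEAP Participants and Siblings together and then repeated in each cohort by the same method, so all three fits include the covariate. I read it as each sampled person's own intake, because SAP 8.3.2 and 8.4.5 derive the variable person by person: "average weekly peanut protein consumption in the 4 weeks prior to V144 for participants in all 4 cohorts".

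Arm for LEAP participants is set "according to the prior randomized treatment assignment from the LEAP study" (SAP section 6); siblings take the arm of their LEAP participant.

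Two places describe the same endpoint without the covariate. In Protocol 9.2.2, household consumption and dust "will be compared between the families of the LEAP avoiders and LEAP consumers using linear mixed effects models with a random family effect included". In SAP Table 3 (section 8.4.1), they "will be compared between the families of the LEAP avoiders and LEAP consumers using linear mixed effects models", again with only a random family effect. SAP section 11 lists two changes from the protocol: the participant ITT sample and the parent PP sample. The dust model is not among them.

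The only other use of dust by arm is in the same section. Dust in LEAP participants at V60, V72 and V144 is to be summarised and plotted, and may be analysed against arm and other factors. That analysis is optional and leaves out siblings.

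**The concern.** Current intake comes after randomisation and can be a consequence of it. The SAP treats it as an outcome: it is compared by arm as secondary endpoint 1 (SAP 8.3.2.1 and 8.3.2.2). SAP 8.4.5 also uses consumption questionnaires as a gauge of environmental peanut exposure in the household. A model that holds own intake fixed therefore asks whether beds differ by arm among people who eat the same amount. That is a different question from how much peanut is in the beds in each arm.

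At stake is how the dust result will be read. A small adjusted contrast could be reported as similar dust exposure in the two arms when it shows only similarity at equal own intake. Conditioning on a post-randomisation variable also gives up the protection of randomisation. Anything that drives both intake and dust, such as a family's eating habits, can then bias the arm coefficient.

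**Working it through.** The plan states no sample size, effect size or power for the dust comparison, so there is no figure to reproduce. The check covers timing, structure and an illustration of size.

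**1. Timing.** LEAP participants must be at least 114 months old (Protocol 4.1.1), and the older example in Protocol 3.1 entered LEAP at 10.9 months. The gap is at least about 114 − 10.9 = 103.1 months, or 103.1/12 = 8.6 years. Intake in the 4 weeks before V144 cannot be a baseline covariate.

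**2. What the coefficient estimates.** Let a be the arm effect on own intake, b the effect of own intake on dust, and c the arm effect on dust by all other routes, including other household members' eating. With linear effects and no shared causes:

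- model without the covariate: c + a·b
- model with the covariate: c

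The two agree if a = 0 or b = 0. Otherwise the adjusted coefficient omits a·b. It is not forced to zero, because c may be non-zero.

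**3. Is a likely to be zero?** The documents do not report V144 intake. Protocol 1.1 gives peanut allergy at 72 months as 18.6% in the avoidance group and 4.8% in the consumption group. Suppose that status persists, allergic children eat no peanut, and everyone else eats the same amount in both arms. Mean intake in avoiders relative to consumers is then (1 − 0.186)/(1 − 0.048) = 0.814/0.952 = 0.855, about 14.5% lower, from allergy alone. The assumptions are mine; the point is only that a difference is plausible.

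**4. Illustrative size.** A simulation fitted the mixed model with a random family effect, with and without own intake. The assumed inputs, none from the documents, were 500 families, 2 or 3 sampled members each, an arm effect on intake of 1 SD, a total arm effect on dust of about 1, and a within-family intake correlation r of 0.2 or 0.6. There were only four replicates per setting, so second decimals are noise. The share removed is 1 − adjusted/unadjusted.

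| Routes to dust (own intake / others' intake / direct) | r | Unadjusted | Adjusted | Share removed |
|---|---|---|---|---|
| 1.0 / 0 / 0 | 0.2 | 0.96 | 0.01 | 99% |
| 1.0 / 0 / 0 | 0.6 | 0.98 | −0.02 | all |
| 0.7 / 0.3 / 0 | 0.2 | 1.00 | 0.30 | 70% |
| 0.7 / 0.3 / 0 | 0.6 | 0.95 | 0.13 | 86% |
| 0.5 / 0.5 / 0 | 0.2 | 0.97 | 0.50 | 48% |
| 0.5 / 0.5 / 0 | 0.6 | 1.00 | 0.27 | 73% |
| 0.3 / 0.7 / 0 | 0.2 | 1.01 | 0.76 | 25% |
| 0.3 / 0.7 / 0 | 0.6 | 0.95 | 0.33 | 65% |
| 0.5 / 0.3 / 0.2 | 0.2 | 1.00 | 0.50 | 50% |
| 0.5 / 0.3 / 0.2 | 0.6 | 0.99 | 0.38 | 62% |
| 0.2 / 0.3 / 0.5 | 0.2 | 0.97 | 0.77 | 21% |
| 0.2 / 0.3 / 0.5 | 0.6 | 0.97 | 0.63 | 35% |

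The unadjusted model recovers the assumed total throughout. The adjusted one falls short in every setting, by about 21% up to all of it. In the 0.5 / 0.5 rows, the part of the effect that bypasses own intake is 0.5 at both correlations, yet the adjusted coefficient drops from 0.50 to 0.27 when family members eat more alike. Own intake then stands in for other members' intake, so the coefficient is not a clean direct effect either.

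**The case against.** The best case for the plan is that the adjusted question is sensible. The covariate is own intake, not household intake, so the model asks whether a bed carries more peanut than its occupant's eating explains. That is close to the sibling rationale of environmental exposure without consumption (Protocol 9.2.1), and Protocol 2.3 asks only that dust be characterised. This stands as a reason to keep the model. It does not justify making it the only committed comparison, since the SAP never labels it as dust beyond own intake.

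Second, intake is itself compared by arm without adjustment, for individuals (SAP 8.3.2) and for all household members (SAP 8.4.5), and participants' dust is summarised and plotted. A careful reader would see any intake difference beside the dust result. This lowers the risk of misreading, but supplies no committed unadjusted arm comparison of dust.

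Third, after years of ad libitum eating the arms may no longer differ in intake, and the two analyses would then nearly coincide. That is possible, and the documents cannot settle it.

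Fourth, Protocol 9.2.2 names a model class and does not exclude covariates, Table 3 is only an overview, and Protocol 9.5 requires an amendment only for principal features. That is fair: this is an unlisted addition, and calling it a breach of the protocol would go too far.

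A reader might also infer that the covariate undermines the sibling hypothesis. The documents do not support that. The sibling exposure objective uses LEAP food frequency questionnaires and dust at the LEAP 60-month visit (Protocol 2.2), and the sibling factor models (SAP 8.2.2.3 and 8.3.9.2) enter V60 and V144 dust as separate candidate terms without using this coefficient.

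**Conclusion.** The concern holds in limited form. Every committed arm model for V144 dust conditions on a variable measured after randomisation and plausibly affected by it. If intake differs by arm at V144, the result is not the total arm difference in dust exposure and is open to bias from shared causes. If it does not differ, little changes.

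It would be tempting to say that the model cannot show any exposure difference, or that intake is the main route from arm to dust. Neither is established: the documents do not quantify the routes, and the effect of other members' intake is only partly removed. The range of about 21% to 100% removed rests on assumed inputs and should not be quoted as an expected loss. The endpoint is exploratory, and the co-primary tests and the V60-based sibling exposure objective are unaffected. The change is still worth making because it is cheap and aligns SAP 8.4.6 with Table 3 and the protocol.

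**What to change.** In SAP 8.4.6, make the mixed model with arm and a random family effect, and no consumption covariate, the main analysis of the dust part of exploratory endpoint 4. Apply it to the combined cohorts and to the participant and sibling repeats. Keep the model adjusted for own consumption as a supplementary analysis, labelled as dust beyond own intake, with a note that it conditions on a post-randomisation variable. Record the addition in SAP section 11. The SAP already follows this order for TEWL in LEAP participants (8.4.4.1), with a plain comparison first and an adjusted model in addition.

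The cost is a few sentences and one extra model run for each of the three cohort analyses. No new data are needed.

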9. SAFETY EVALUATION

9.1. Adverse Events

Safety will be analyzed through the reporting and analysis of AEs. All AEs will be classified by body system and preferred term according to Medical Dictionary for Regulatory Activities (MedDRA) version V21.1. The severity of AEs will be classified using the National Cancer Institute Common Terminology Criteria for Adverse Events (NCI-CTCAE) toxicity scale.

Adverse events will be collected from participants in all 4 cohorts (LEAP Participants, Older Siblings, Younger Siblings, and Parents) from the time the participant signs the informed consent until 30 days after study procedures are performed. Since the LEAP Trio study consists of a single planned study visit, the principal aim is to capture adverse events that may be related to study procedures such as venipuncture, home self blood collection, skin-prick testing, assessment of TEWL, and oral food challenges. Oral food challenges will be conducted in LEAP Participants and LEAP Siblings < 18 year of age.

All safety analyses will be carried out using the ITT sample unless otherwise noted. Missing safety information will not be imputed.

AE summary tables will include counts of participants. If a participant experiences more than one episode of a particular AE, the participant will be counted only once for that event. If a participant has more than one AE that codes to the same preferred term, the participant will be counted only once for that preferred term. Similarly, if a participant has more than one AE within a body system category, the participant will be counted only once in that body system category. In AE summaries, body systems and preferred terms within each body system will be arranged by descending total frequency across the treatment groups. Percent of participants experiencing AEs in each body system and preferred term will be presented.

An overall summary table will be developed to report the number of events and the number and percentage of participants having at least one event in the following categories, presented by LEAP Trio cohort and treatment arm and overall:

- AEs
- AEs indicated as serious (SAEs)
- AEs with an outcome of death
- AEs reported by maximum severity
- AEs reported by relationship to study procedure
- AEs reported by action taken with study procedure

In addition, adverse events classified by MedDRA system organ class and preferred term will be summarized for each LEAP Trio cohort and overall for each of the following:

- All AEs
- AEs by maximum severity

